6.14.6.4. Conjunctivitis

Conjunctivitis are events of special interest and will be identified using PTs nested within the categories of conjunctivitis and Keratitis as described in the Compound Level Safety Standards:

Table KGAC.6.20. Summary Tables/Listing Related to Conjunctivitis

Analysis	Population
Summary of TEAE of conjunctivitis within categories	mS, mA
Summary and/or listing of conjunctivitis and eye inflammation follow-up form	mS (summary only)
A listing of patients with conjunctivitis	S

Abbreviations: mA = All Lebrikizumab Modified Safety Population; mS = Modified Safety Population; TEAE = treatment-emergent adverse event.

6.14.6.5. Hypersensitivity

Potential hypersensitivity reactions will be determined using the following SMQs: anaphylactic reaction, hypersensitivity, and angioedema. Potential hypersensitivity will be categorized as immediate (ie, occurring the same day as drug administration) and non-immediate (ie, occurring after the day of study drug administration but prior to subsequent drug administration). The planned summaries are provided in [Table KGAC.6.21](#).

Table KGAC.6.21. Summary Tables Related to Hypersensitivity

Analysis	Population
for immediate hypersensitivity: (1) combined narrow/algorithmic search (ie, any narrow term from any one of the SMQs, or anaphylaxis algorithm); (2) narrow search (ie, any narrow term) by SMQ; (3) broad search (ie, any narrow or broad term) by SMQ; and (4) TEAEs (occurring on the day of study drug administration) by PT not in any of the 3 SMQs	mS, mA
for nonimmediate hypersensitivity: (1) combined narrow search (ie, any narrow term from any one of the SMQs); (2) narrow search (ie, any narrow term) by SMQ; and (3) broad search (ie, any narrow or broad term) by SMQ	mS, mA

Abbreviations: mA = All Lebrikizumab Modified Safety Population; MedDRA = Medical Dictionary for Regulatory Activities; mS = Modified Safety Population; PT = Preferred Term; SMQ = Standardised MedDRA Query; TEAE = treatment-emergent adverse events.

6.14.6.6. Injection Site Reactions (ISR)

Injection site reactions (ISRs) are AEs localized to the immediate site of the administration of a drug. The evaluation of study drug related ISRs will be through the unsolicited reporting of ISR TEAEs. Injection site reactions will be defined using the MedDRA High Level Term (HLT) of Injection Site Reaction, excluding certain PTs related to joints as described in the Compound Level Safety Standards.

Table KGAC.6.22. Summary Tables Related to Injection Site Reactions

Analysis	Population
Summary of TEAE of ISR overall and by PT	mS, mA

Abbreviations: HLT = High Level Term; ISR = injection site reaction; mA = All Lebrikizumab Modified Safety Population; mS = Modified Safety Population; PT = Preferred Term; TEAE = treatment-emergent adverse event.

6.14.6.7. Malignancies

Malignancies will be defined using PTs from the Malignant tumors SMQ and summarized separately for the 2 categories: Nonmelanoma skin cancer (NMSC) and Malignancies excluding NMSC as below.

Table KGAC.6.23. Summary Tables Related to Malignancies

Analysis	Population
Summary of TEAE of malignancies within categories of NMSC and malignancy excluding NMSC	mS, mA

Abbreviations: mA = All Lebrikizumab Modified Safety Population; mS = Modified Safety Population; NMSC = nonmelanoma skin cancer; TEAE = treatment-emergent adverse event.

6.14.6.8. Atopic Dermatitis Exacerbation

Atopic dermatitis exacerbation will be defined using PTs specified in the Compound Level Safety Standards and summarized below:

Table KGAC.6.24. Summary Tables Related to Atopic Dermatitis Exacerbation

Analysis	Population
Summary of TEAE of atopic dermatitis exacerbation	mS, mA

Abbreviations: mA = All Lebrikizumab Modified Safety Population; mS = Modified Safety Population; TEAE = treatment-emergent adverse event.

6.14.6.9. Suicide/Self-Injury Standardised Medical Dictionary for Regulatory Activities Query

Suicide/self-injury will be defined as described in the Compound Level Safety Standards and summarized below.

Table KGAC.6.25. Summary Tables Related to Suicide/Self-Injury Standardised Medical Dictionary for Regulatory Activities Query

Analysis	Population
Summary of TEAE of Suicide/self-injury SMQ	mS, mA

Abbreviations: mA = All Lebrikizumab Modified Safety Population; mS = Modified Safety Population; TEAE = treatment-emergent adverse event.

6.15. Subgroup Analyses

6.15.1. Efficacy Subgroup Analyses

Subgroup analyses will be conducted for the primary endpoints IGA 0/1, EASI-75, EASI-90, and 4-point improvement in Pruritus NRS at Week 16 in the mITT Population using MCMC-MI approach as in primary analysis (Section 6.4.1.1). A logistic regression analysis with treatment, subgroup, and treatment-by-subgroup interaction as factors will be used. The treatment-by-subgroup interaction will be tested using the Firth correction (Firth 1993) at the 10% significance level. Treatment group differences will be evaluated within each subgroup using the chi-square test, regardless of whether the interaction is statistically significant. If any group within the subgroup (eg, yes, no) is <10% of the total population, only descriptive statistics will be provided for that subgroup (ie, no inferential testing).

Forest plots may be created to illustrate the treatment differences with 95% CIs between each of the lebrikizumab treatment groups and placebo group, by each subgroup category.

The following subgroups will be analyzed:

- Age group (Adolescents (12 to <18), Adults ≥ 18)
- Age group (Adolescents (12 to <18), Adults ≥ 18 to < 65, ≥ 65 to < 75, ≥ 75)
- Sex (male, female)
- Race (American Indian or Alaska Native, Asian, Black or African American, Native Hawaiian or Other Pacific Islander, White, Multiple, Other, Not Reported)
- Ethnicity (Hispanic or Latino, Not Hispanic or Latino, Not reported, Unknown)
- Region (as defined in Section 6.5)
- Weight category (<60 kg, ≥ 60 to <100 kg, ≥ 100 kg)
- BMI category (Underweight ($<18.5 \text{ kg/m}^2$), Normal (≥ 18.5 and $<25 \text{ kg/m}^2$), Overweight (≥ 25 and $<30 \text{ kg/m}^2$), Obese (≥ 30 and $<40 \text{ kg/m}^2$), Extreme obese ($\geq 40 \text{ kg/m}^2$))
- Duration since AD onset category (0 to <2 years, 2 to <5 years, 5 to <10 years, 10 to <20 years, ≥ 20 years)
- Baseline IGA 3 versus 4
- Baseline pruritus <4 versus ≥ 4
- Prior use of systemic treatment (yes, no)

Some additional subgroup analyses may be added to meet regulatory requirements. The analysis of additional subgroups will not require an amendment to the SAP.

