5.2. Determination of Sample Size

For FDA: In the DRM06-AD01 Phase 2b study (J2T-DM-KGAF), the proportion of patients who achieved an IGA score of 0 or 1 at Week 16 using the rescue medication non-response sensitivity analysis was approximately 34.7% for lebrikizumab 250 mg Q2W versus 7.7% for placebo. A sample size of 96 for lebrikizumab 250 mg Q2W versus 48 for placebo will have more than 95% power to detect a statistically significant difference based on a two group continuity corrected chi-square test with a two-sided significance level of 0.05. However, to ensure sufficient safety information is collected and to ensure sufficient responders for the Maintenance Period, the sample size will be increased to approximately 400 in total with a randomization ratio of 2:1 lebrikizumab:placebo.

For European Medicines Agency (EMA): In the DRM06-AD01 Phase 2b study (J2T-DM-KGAF), the proportion of patients who achieved an IGA score of 0 or 1 at Week 16 using the rescue medication non-response sensitivity analysis was approximately 34.7% for lebrikizumab 250 mg Q2W versus 7.7% for placebo, and the proportion of patients who achieved an EASI-75 at Week 16 using the rescue medication non-response sensitivity analysis was approximately

48.0% for lebrikizumab 250 mg Q2W versus 11.5% for placebo. A sample size of 96 for lebrikizumab 250 mg Q2W versus 48 for placebo will have more than 95% power to detect a statistically significant difference based on a two-group continuity corrected chi-square test with a two-sided significance level of 0.05 for each of the co-primary endpoints, which imply an overall power of at least 90%. However, to ensure sufficient safety information is collected and to ensure sufficient responders for the Maintenance Period, the sample size will be increased to 400 in total with a randomization ratio of 2:1 lebrikizumab:placebo.

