6.1.2. General Considerations for Analyses During Induction Period

Induction Period starts after the first injection of study treatment at Baseline Visit (Day 1) and ends prior to the first injection of study treatment at Week 16 or the early termination visit (ETV) (between Day 1 and Week 16). For patients who are randomized but not dosed, the Induction Period starts on the date of randomization.

Baseline will be defined as the last available value before the first injection for efficacy and health outcome analyses. In most cases, this will be the measure recorded at Baseline Visit (Day 1). If the patient does not take any injection, the last available value on or prior to randomization date will be used. Change from baseline will be calculated as the visit value of interest minus the baseline value.

For Pruritus Numeric Rating Scale (NRS) and Sleep-Loss due to Pruritus collected via eDiary, the baseline period is the 7-day window prior to the first injection. A patient must have responses on at least 4 of 7 days to calculate a baseline weekly mean. If a patient has 3 or fewer responses, the baseline mean value will be considered missing. eDiary data for Pruritus NRS and Sleep-loss due to Pruritus are mapped to study visit per [Appendix 1](#).

For the safety analyses, the following baselines will be used. For safety analyses using a baseline period, the baseline period is defined as the time from Screening Visit to the date/time of the first injection in Induction Period.

- Treatment-emergent adverse events (TEAEs): baseline will be all results recorded during the baseline period.
- Treatment-emergent abnormal laboratory and vital signs results: baseline will be all results recorded during the baseline period.
- Change from baseline to last post-baseline observation or to each scheduled post baseline visit for laboratory and vital signs results: baseline will be the last scheduled non-missing assessment recorded during the baseline period.

The randomization to treatment groups is stratified by geographical region (US versus EU versus rest of world), age (adolescent patients 12 to <18 years versus adults ≥ 18 years) and baseline disease severity (IGA 3 versus 4) as described in Section [5.3](#). The countries will be categorized into geographic regions for analysis (Section [6.3](#)). Unless otherwise specified, the statistical analysis models for Induction Period will adjust for geographic region, age and baseline disease severity.

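### The efficacy subgroup analyses leave out the randomisation factors that the primary analysis adjusts for; adding them as main effects is a small, low-cost improvement

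*SAP*

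**What the plan says.** SAP Section 6.15.1 covers IGA 0/1, EASI-75, EASI-90 and the 4-point pruritus response at Week 16 in the modified ITT population, with the primary analysis's multiple imputation. The model is given as: "A logistic regression analysis with treatment, subgroup, and treatment-by-subgroup interaction as factors will be used". The interaction is tested with the Firth correction at the 10% level. Then: "Treatment group differences will be evaluated within each subgroup using the chi-square test", whatever the interaction test shows. Levels holding less than a tenth of the patients are only described. The subgroup list includes age, region and baseline IGA, and also sex, race, weight, BMI, disease duration and prior systemic treatment, among others.

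Elsewhere the three factors are used throughout. Randomisation is stratified by them (Protocol 5.3, SAP 5.3) and the primary CMH test adjusts for them (Protocol 9.2). SAP 6.1.2 sets a default: "Unless otherwise specified, the statistical analysis models for Induction Period will adjust for geographic region, age and baseline disease severity". SAP 6.3 repeats it for induction efficacy and health outcome models.

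The SAP revision history for Version 2 explains why the within-subgroup test changed from Fisher's exact to chi-square: so that imputed results can be pooled with PROC MIANALYZE. It gives no reason for leaving out the strata. Appendix 2 already pools a stratified risk difference, odds ratio and CMH statistic through that procedure.

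**The concern.** Stratified randomisation balances region, age and IGA over the whole trial, but not inside a subgroup such as sex or weight band. There the arms can differ by chance in baseline severity, and an unadjusted difference moves with that imbalance. If baseline IGA predicts response, adjustment removes part of this noise and gives the interaction test a little more power.

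Consistency is also at stake. The primary result is a stratum-adjusted risk difference, whereas the subgroup results would be crude. The reader is not told whether Section 6.15.1 sets the Section 6.3 default aside on purpose.

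**Working it through.** **The plan's own figure.** The documents give no power or precision for subgroups, so the check starts from SAP 5.2: "A sample size of 96 for lebrikizumab 250 mg Q2W versus 48 for placebo will have more than 95% power", "based on a two group continuity corrected chi-square test with a two-sided significance level of 0.05", with IGA rates of "approximately 34.7% for lebrikizumab 250 mg Q2W versus 7.7% for placebo".

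- Pooled rate: (48 × 0.077 + 96 × 0.347)/144 = 0.257.
- Null SE: √[0.257 × 0.743 × (1/48 + 1/96)] = 0.0773. Alternative SE: √(0.077 × 0.923/48 + 0.347 × 0.653/96) = 0.0620.
- Uncorrected: Φ[(0.270 − 1.96 × 0.0773)/0.0620] = 97.2%. With the continuity correction 0.5 × (1/48 + 1/96) = 0.0156 subtracted: 95.2%. Exact enumeration of the corrected test gives 95.5%.

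The stated figure reproduces.

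**Chance imbalance inside a subgroup.** Assume 40% of patients have IGA 4. With overall balance held by stratification, the SD of the between-arm difference in the IGA 4 share is about √[0.4 × 0.6 × (1/n₁ + 1/n₀) × (1 − f)], where f is the subgroup's share of 400.

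- f = 0.5 (133 v 67): 5 percentage points.
- f = 0.15 (40 v 20): 12 points. Simulation gave about 5 and 13.

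**Interaction test.** Simulated trials of 400 patients (the planned size is "increased to approximately 400 in total with a randomization ratio of 2:1 lebrikizumab:placebo"), randomised in blocks within 3 × 2 × 2 = 12 strata, with the IGA rates above. Not in the documents, so assumed: region shares 45/30/25%; IGA 4 in 40%; subgroup independent of the strata; true interaction odds ratio 0.4. The odds ratios for IGA 4 v 3, adolescent and EU were 1/1/1 (none), 0.5/1.2/1.2 (moderate) or 0.33/1.5/1.5 (strong). Firth model, 10% level:

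| Subgroup share | Prognosis | Interaction log OR, without → with factors | SE | Power |
|---|---|---|---|---|
| 50% | none | −0.91 → −0.91 | 0.739 → 0.736 | 35.8 → 36.2% |
| 50% | moderate | −0.90 → −0.92 | 0.741 → 0.741 | 35.3 → 36.5% |
| 50% | strong | −0.88 → −0.93 | 0.740 → 0.747 | 32.8 → 34.6% |
| 12% | none | −1.01 → −1.01 | 1.188 → 1.184 | 27.1 → 27.0% |
| 12% | moderate | −1.04 → −1.06 | 1.177 → 1.182 | 26.0 → 26.8% |
| 12% | strong | −0.98 → −1.03 | 1.177 → 1.195 | 25.3 → 26.6% |

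The SE does not shrink. The estimate moves away from zero, and the power gain comes from that. With no true interaction, rejection rates were 4.5 to 8.6% without the factors and 4.8 to 8.4% with them.

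**Standardised difference from one model on all patients.** In a further simulation of 1,000 runs per setting, one Firth model was fitted to all 400 patients with the factors as main effects, and subgroup risk differences were standardised from it. It was compared with the same Firth model without the factors.

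- IGA 4 log-odds −1.1 to −1.5: variance of the subgroup difference 1 to 4% lower; interaction power up 1 to 5 points.
- IGA 4 log-odds 0 to −0.7: variance changed by about 1% or less; power moved by −1 to +2 points.
- False positives at or below 10%.

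A separate set of runs at log-odds −1.1 to −1.5 also used the EASI-75 rates ("48.0% for lebrikizumab 250 mg Q2W versus 11.5% for placebo"). It gave variance reductions of 2 to 6% and, in 50% subgroups, power gains of 2 to 3 points for IGA and 3 to 6 for EASI-75. In 15% subgroups the power gain was 0 to 3 points.

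**Two versions that do not help in small subgroups.** A 12% subgroup has 0.12 × 400 = 48 patients, about 32 v 16, or four per stratum on average.

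- 12-stratum CMH instead of chi-square: power 53.4 → 45.9% (moderate or strong prognosis) and 55.4 → 47.1% (none). About 13% of patients fall in one-arm strata. The risk-difference SD rises from 0.109 to 0.124 (moderate). In a 50% subgroup almost nothing changes (99.9 → 99.6% moderate, 99.3 → 99.5% strong).
- Adjusted Firth model fitted separately inside the subgroup: SD 0.1019 → 0.1043 (moderate), so variance × (0.1043/0.1019)² = 1.05.

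**The case against.** The default in Section 6.1.2 allows exceptions, and Section 6.15.1 states its own terms, so the two do not contradict each other. That stands: this is an unexplained departure, not an inconsistency in the rules.

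A simple chi-square is defensible where groups may be as small as 40 patients. That also stands. In the 12% subgroup it had 53 to 55% power, against 25 to 26% for a Wald test from an unadjusted Firth model fitted inside the subgroup and 30 to 32% for the adjusted one. Keeping the chi-square as a supportive result is sensible.

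The SAP gives pooling with PROC MIANALYZE as its reason for the chi-square. This explains the move away from Fisher's exact test but not the missing strata, because Appendix 2 pools stratified statistics in the same way.

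A reader might infer more than the documents support:

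- That every other induction analysis adjusts for the strata. It does not: Section 6.1.2 uses Fisher's exact test and an ANCOVA on treatment and baseline only for safety.
- That a forest plot will set crude subgroup differences beside the stratified overall result. Such plots are optional, and Section 6.15.1 mentions no overall row.
- That precision is being thrown away for no reason. The gain is small, close to nil if baseline IGA is weakly prognostic, and the wrong form of adjustment makes small subgroups worse.

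**Conclusion.** The omission is real and departs from the adjustment used in the primary CMH test and set as the default for induction efficacy models. The benefit of correcting it is minor: about 0 to 5% lower variance of the subgroup difference (at 5%, a confidence interval narrower by 1 − √0.95 = 2.5%) and about 0 to 5 points more power for the 10% interaction test. Individual simulated settings ran from −1 to +6 points.

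These figures rest on assumed prognostic strength, strata shares and subgroup sizes, none of which the documents give, and on 400 patients. The modified ITT population excludes one site and is somewhat smaller.

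A reader might take this as a flaw in validity. The simulations do not support that: false-positive rates are controlled either way. Age, region and IGA each enter the model when they are the subgroup, and the subgroup tests lie outside the multiplicity scheme of Section 6.6. No primary or major secondary conclusion is affected.

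**What to change.** In Section 6.15.1:

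1. Add region, age group and baseline IGA as main effects to the Firth interaction model, fitted to all modified ITT patients, omitting whichever factor defines the subgroup.
2. For each subgroup level s, report the standardised risk difference RD_s = (1/n_s) Σ [p̂(active, s, z_i) − p̂(placebo, s, z_i)], summed over the n_s patients in that level, where z_i are the patient's stratification factors. Obtain a delta-method variance in each of the 25 imputed data sets and pool with PROC MIANALYZE.
3. Keep the unadjusted chi-square as a supportive result, labelled as unadjusted.
4. Do not apply the 12-stratum Mantel-Haenszel or CMH analysis inside small subgroups.

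If the planned model is kept, one sentence should say that the Section 6.3 adjustment is deliberately set aside and that subgroup estimates are unadjusted.

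The cost is slight extra programming, mainly the delta-method variance in each imputation. SAP Version 5 was approved after the study team was unblinded to induction treatment, so a change made now should be labelled as added after that point.

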6.15.2. Safety Subgroup Analyses

Subgroup analysis for safety related endpoints will be performed within the context of the integrated safety analysis. No safety subgroup analysis will be performed specifically for this study unless there is a potentially relevant finding during the periodic study safety reviews.

6.16. Protocol Deviations

Protocol deviations will be identified throughout the study. Important protocol deviations are defined as those deviations from the protocol likely to have a significant impact on the completeness, accuracy, and/or reliability of the study data or that may significantly affect a patient's rights, safety, or well-being.

Potential examples of important protocol deviations include patients who violated the inclusion/exclusion criteria, used an interfering concomitant medication, significant non-compliance with study medication (<75% of expected injections). Refer to a separate document called "KGAC Trial Issues Management Plan" for the important protocol deviations with categorizations.

The number and percentage of patients having IPD(s) will be summarized within category and subcategory of deviation by treatment group for Induction Period using the ITT population and for Maintenance Period using all the Maintenance Populations (including Maintenance Primary Population, Maintenance Secondary Population and Maintenance W16 Escape Population).

A by-patient listing of important protocol deviations will be provided for the ITT population.

6.16.1. Impact of COVID-19

Impact of pandemic (eg, COVID-19) on analyses may be addressed prior to study unblinding at Week 16 DBL, once the impact on study conducts are fully understood. In general, any missing assessments/visit window will be documented as protocol deviations. For patients who have missing assessments at Week 16 due to COVID-19, these patients may enter the escape arm. A summary or listing may be provided to summarize missing visits due to COVID-19.

Treatment discontinuation due to pandemic will be treated the same type of intercurrent event as treatment discontinuation due to reasons other than lack of efficacy. Strategies of how this type of intercurrent event will be handled are described in Section 6.2. Intermittent missing assessment due to pandemic will be treated the same as any other intermittent missing values. Details of how missing data will be handled are described in Section 6.4.

6.17. Interim Analyses and Data Monitoring

Data Monitoring Committee/Data Safety Monitoring Board (DMC/DSMB): The lebrikizumab Phase 3 AD programs' DSMB is an independent expert advisory group commissioned and charged with the responsibility of evaluating cumulative safety at regular intervals, as well as on an ad hoc basis, as needed. The DSMB will consist of members external to Lilly and follow the rules defined in the DSMB charter, focusing on potential and identified risks for this molecule. Data Monitoring Committee membership will include, at a minimum, a physician with expertise in dermatology and a statistician. No member of the DSMB may have contact with study sites. This committee will make recommendations as to a) continue the clinical studies without modification; or b) continue the clinical studies with modifications; or c) terminate one or more of the clinical studies. Details outlining the roles and responsibilities of the DMC are documented in the "Dermira DRM06 DSMB Program Charter" and the planned analyses are outlined in the DMC analysis plan prior to the first unblinded assessment.

Access to the unblinded safety data will be limited to the DSMB. The study team will not have access to the unblinded data. Only the DSMB is authorized to evaluate unblinded data. The purpose of the DSMB is to advise Lilly regarding patient safety; however, the DSMB may request key efficacy data to put safety observations into context and to confirm a reasonable benefit/risk profile for ongoing patients in the study. Hence, there will be no alpha adjustment for these interim assessments.

Week 16 Database lock (DBL): An unblinded interim analysis will be performed at the time (ie, a cut-off date) the last patient completes Week 16 or the ETV from the study. This database lock will include all data collected by the cut-off date. Only the Induction Period treatment assignment will be unblinded at the time of this interim lock. Maintenance Period treatment assignment will remain blinded.

Week 52 DBL: Another unblinded interim analysis will be performed at the time (ie, a cut-off date) the last patient completes Week 52 or the ETV from the study. This database lock will

include all data collected by the cut-off date and is the final analysis for the efficacy endpoints up to Week 52.

The study will not be terminated early on the basis of efficacy following these interim analyses.

Final DBL: A final DBL will occur after all patients have completed the safety follow-up period of the study, discontinued current study, or enrolled into the long-term extension study DRM06-AD07.

Depending on the regulatory submission timeline, the Week 52 DBL and the final DBL may be combined, ie, one final DBL will occur after all patients have either completed the follow-up period of the study discontinued the study early, or entered the long-term extension study DRM06-AD07.

